2.2 Aims

Healthcare technology assessment is the multidisciplinary evaluation of medical technologies with regard to **feasibility, safety, efficacy**, indications for use, cost, and cost-effectiveness. A complete assessment should explore the scientific, ethical, economic, and social reasons for adopting a technology and it may influence the quality of service and distribution of resources.

In this multicenter study, we aim to assess the first 3 important criteria.

Aim 1 – To determine the **feasibility** of using a wireless system immediately after delivery and for the first 2h of age, while in the obstetrical center under unsupervised parents' care. The following outcomes will be measured for both wired and wireless systems:

- a. Percentage of time for which HR, RR, SpO₂ and T_{skin} data are displayed.
- b. Occurrence of gaps in signal detection/recordings (% and length).
- c. Causes of the gaps in signal detection/recordings.
- d. Descriptive analysis of user surveys and their satisfaction with the wireless system.

Aim 2 - To investigate the **safety** of using this wireless system immediately after delivery and for the first 2h of age. The following outcomes will be measured for both wired and wireless systems:

- a. Skin score to be determined by a blinded dermatologist using de-identified pictures of the skin after removal of the sensors of each system.
- b. Pain scale to assess any discomfort or pain during the removal of the sensors.
- c. Clinically significant events detected by the wired system (HR < 100 bpm or SpO₂ < 80%) but missed by the wireless system.

Aim 3 – To assess the **accuracy** of this wireless system in measuring HR, RR, SpO₂ and T_{skin} signals compared with the “standard of care” wired system. The following outcomes will be computed:

- a. Correlation coefficient
- b. Slope
- c. Variance accounted for
- d. Bias

Further subgroup analyses will be conducted to assess for systematic differences in feasibility, safety, and accuracy of the wireless system between the following:

- High vs. Low and Middle income countries
- Female vs. Male subjects
- Term vs. Preterm (born < 37 weeks gestational age) infants
- C-section vs. Vaginal delivery

- Skin pigmentation

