3.3.4 Data Collection

The Study research team at each site will collect standard demographic and clinical information from mothers and newborns as described in the Data Collection Form (see Appendix 1) during the 2hrs of vital sign recording (see Figure 11 below). With a stopwatch, a designated trained research team member(s) will time the recording as the period (sec.) that elapses from the application of the leads until the first display of data on the monitors, for all the sensors of both systems. Data will be continuously recorded while the mother/caregiver provides routine care. Annotations as described in the Data Collection Form will be documented by the research team regarding movements, breast-feeding attempts, cleaning/drying, patting, etc. (see Appendix 1). The vital signs data displayed on the monitors will only be visible to designated research team member(s), and all alarms will be turned off so as not to disturb parents and newborn. Any clinically relevant changes observed in vital sign parameters will be communicated by the research team member(s) to the obstetrical/neonatal team. A clinically relevant event is defined as follows: HR < 100 bpm or SpO₂ <85% (after the first 10 minutes of life) with sinusoidal wave as detected on either monitoring system during the course of the 2hr continuous monitoring. If the neonate requires any intervention to reverse instability, such as oxygen therapy and ventilator support, data collection will end but the data collected up to that time point will be included. The participating baby will not be withdrawn from the study.

The following data will be collected:

- Skin assessment:* In order to assess the safety of the wireless skin sensors, photographs of the infant's skin will be taken before device placement and after device removal. Each participating site will send de-identified digital photos coded (with the participant's study code) to the dermatologist for blinded assessment using the skin score (Neonatal Skin Condition Score - NSCS) as described in the Data Collection Form.
 - **Neonatal Skin Condition Score (NSCS)³⁷:** Photographs of the infant's skin at the site of device placement for both the chest and limb skin sensors will be taken prior to device

placement and following device removal. These photographs will then be scored by a dermatologist using the NSCS. Scores range from 3 (intact skin condition) to 9 (very poor skin condition).

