8. ADVERSE EVENTS RELATED TO MONITORING

WIRED SENSORS

- None
- Skin irritation: () Chest or () Limb
- Skin erosions: () Chest or () Limb
- Skin bleeding: () Chest or () Limb

Skin photos: Chest Limb

Neonatal Skin Condition Score (NSCS)*
Chest: Limb:

WIRELESS SENSORS

- None
- Skin irritation: () Chest or () Limb
- Skin erosions: () Chest or () Limb
- Skin bleeding: () Chest or () Limb

Skin photos: Chest Limb

Neonatal Skin Condition Score (NSCS)*
Chest: Limb:

Treatment required: Yes: () No

Chest Neonatal Skin Condition Score (NSCS)* will be done by a blinded dermatologist at the end of the AWARD project.

Signature of data collector: _____

Date (YYYYMMDD): _____

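### Aim 2a defines the skin outcome on post-removal pictures only, and no outcome or analysis uses the pre-placement photographs, so existing findings can be attributed to the sensors

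*Combined protocol and SAP*

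**What the plan says.** Three places in the combined protocol and SAP bear on the skin score, and they do not match.

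- **Section 2.2, Aim 2a.** This is the only definition of the skin safety outcome: a blinded dermatologist assigns the score "using de-identified pictures of the skin after removal of the sensors of each system". The lead-in to Aim 2 applies it to each system: "The following outcomes will be measured for both wired and wireless systems". No baseline is mentioned.
- **Section 3.3.4, skin assessment.** Here "photographs of the infant's skin will be taken before device placement and after device removal", at both the chest and the limb sites. The text then states: "These photographs will then be scored by a dermatologist using the NSCS". The scale runs from 3 (best) to 9 (worst).
- **Appendix 1, item 8 (adverse events related to monitoring).** For each system there is one NSCS entry for chest and one for limb, not marked as pre or post. The footnote says that the scoring "will be done by a blinded dermatologist at the end of the AWARD project".

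Section 4 covers demographics and accuracy, and its sample-size text covers signal coverage and agreement. It gives no analysis of the skin score: no use of baseline, no definition of a new finding, no threshold and no paired comparison. Section 3.3.2.2 excludes only a skin abnormality that would prevent sensor placement.

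**The concern.** The NSCS (Appendix 3) adds items for dryness, erythema and breakdown. Dryness and erythema are not specific to adhesives, and the eligibility criteria let infants with mild findings enter. A score above 3 after removal may therefore reflect the sensor, or skin that already looked that way.

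An analyst who follows Aim 2a and the form will have one number per location and system, filed under monitoring-related adverse events, with no rule for separating the two explanations. Three results are exposed:

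- **The absolute statement per system.** Section 2.1 asks whether the wireless system is safe in itself. The wired comparator does not protect that statement.
- **The safety subgroups in Section 2.2.** If skin before placement differs by gestation, delivery mode, country income level or pigmentation, a post-removal score cannot separate that difference from a difference in sensor effect.
- **The wired-wireless contrast, to a lesser degree.** Both systems are on the same infant, but on separately recorded sites and applied at different ages.

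**Working it through.** **1. Does the plan give a figure to reproduce?** No. It states no rate, margin, power or sample size for the skin score. The check is therefore a comparison of passages plus an illustration.

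**2. Passages side by side**

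| Question | Section 2.2, Aim 2a | Section 3.3.4 | Appendix 1, item 8 | Section 4 |
|---|---|---|---|---|
| Pre-placement photograph? | not mentioned | yes | not distinguished | not mentioned |
| Pre-placement score? | no | yes, on plain reading | no separate field | not mentioned |
| Use of baseline? | none | none stated | none | none |

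The baseline is collected and probably scored, but it enters no outcome and no analysis.

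**3. Illustration of size.** All rates are assumed. Let p be the share of infants with a score above 3 before placement, and q the share of the remaining infants in whom the sensor causes a new finding. Assume that every pre-existing finding is still present at removal.

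- Share above 3 after removal: p + (1 − p)q
- Part of that share that is pre-existing: p / [p + (1 − p)q]

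With the planned 600 infants:

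| p | q | Pre-existing, n | New, n | Above 3 after removal, n | Pre-existing share |
|---|---|---|---|---|---|
| 2% | 1% | 12 | 5.9 | 17.9 | 67% |
| 2% | 3% | 12 | 17.6 | 29.6 | 40% |
| 5% | 1% | 30 | 5.7 | 35.7 | 84% |
| 5% | 3% | 30 | 17.1 | 47.1 | 64% |
| 10% | 1% | 60 | 5.4 | 65.4 | 92% |
| 10% | 3% | 60 | 16.2 | 76.2 | 79% |
| 20% | 1% | 120 | 4.8 | 124.8 | 96% |
| 20% | 3% | 120 | 14.4 | 134.4 | 89% |

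Example, row 2: 0.02 + 0.98 × 0.03 = 0.0494, and 0.02 / 0.0494 = 0.40.

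**4. Sensitivity to persistence.** Suppose only half of the pre-existing findings remain at removal and the other half return to 3. At p = 2%, q = 3% the share is 0.01 / (0.01 + 0.0294) = 25%. At p = 20%, q = 1% it is 0.10 / (0.10 + 0.008) = 93%.

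**5. Change score or adjustment?** For one site, with equal pre and post variances and correlation ρ, the variance relative to the raw post score is 2(1 − ρ) for a simple change and 1 − ρ² for the adjusted post score. At ρ = 0.5 these are 1.00 and 0.75; at ρ = 0.8 they are 0.40 and 0.36. Adjustment is never worse, and a simple change gains nothing at ρ = 0.5. These values of ρ are assumed. The figures describe one score against its own baseline and do not carry over to the wired-wireless difference, which depends on the correlation of the paired differences.

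**The case against.** A reader might infer that skin is scored only after removal and that changes already present will be counted as sensor harm. The documents support neither. Section 3.3.4 names both sets of photographs and then has them scored. No section sets a threshold for an abnormal score or a rule that attributes the raw post-removal score to the sensor. Taking a picture before placement suggests that a before-and-after reading was intended.

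Other points on the same side:

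- **The form does not prove that the baseline is lost.** It has no pre/post split for the photographs either, although both are clearly required. The images are stored in REDCap (Sections 3.3.4 and 3.3.5) and can still be scored in pairs. This stands; the gap is in definition, not in data.
- **Safety does not rest on the NSCS alone.** Item 8 also records irritation, erosions and bleeding by site and system. This stands, though it does not tell a reader how to interpret the NSCS.
- **Each infant carries both systems.** The NSCS grades erythema by share of body surface, so generalised redness would tend to raise both scores. This protects the contrast in part, but not the absolute rate.
- **The error overstates harm.** For the absolute rate, yes: it would not give false reassurance. For the contrast and the subgroups the direction is not fixed, because it depends on where the existing findings lie.
- **Baselines are taken at different ages.** In vaginal births the wireless system goes on at once and the wired system after 10–20 minutes of age; order is randomised only for C-section (Section 3.3.3). A simple change score could build that age difference into the comparison. This is a real limit on the remedy.

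**Conclusion.** The point holds in a limited form. The only stated skin outcome uses post-removal pictures, the form has one unmarked score per location and system, and neither the outcome nor the analysis uses a baseline that Section 3.3.4 already provides. Misattribution is possible but not prescribed. It would fall mainly on absolute per-system rates and on subgroup comparisons, and less on the within-infant contrast.

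Its size cannot be derived from the documents. The illustrative range, about 40% to 96% of post-removal scores above 3, rests wholly on assumed rates (2–20% pre-existing, 1–3% new onset) and on persistence to removal. It shows that the pre-existing share need not be negligible even when few infants have findings at baseline; it is not an estimate for this study. The change is worth making because the data needed are already being collected.

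**What to change.** 1. **Section 2.2, Aim 2a:** define the outcome as a new or worsened NSCS relative to the pre-placement photograph, at each sensor site and for each system.
2. **Section 4:** state a within-infant comparison of the two systems, with the post-removal score adjusted for the pre-placement score at the same site, in preference to a simple change score. Apply the same baseline-referenced outcome in the safety subgroups.
3. **Appendix 1, item 8:** provide separate pre and post NSCS fields for chest and limb under each system, so that the form agrees with Section 3.3.4.
4. **Reporting:** note that in vaginal births the wireless baseline is taken at an earlier age than the wired one, and read the contrast with that in mind.

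The cost is small: revised wording, four more score fields per infant (two locations × two systems) and a slightly longer analysis. No new photographs are needed and, on the plain reading of Section 3.3.4, no new scoring. The change should be made before the end-of-project scoring, so that the choice between a post-only and a baseline-referenced outcome is not made after the scores are known.

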3.3.3 Study Interventions

Each newborn enrolled in the Study will be monitored simultaneously by both the standard of care (control) wired vital sign monitoring system (Infinity M540 monitor, Draeger, Germany) and the wireless monitoring system (intervention) (ANNE Arc chest sensor, SIBEL Health, Illinois, USA and Limb sensor (RAD7, Masimo) (Figure 9).

Both monitoring systems, will simultaneous record heart rate, respiratory rate, oxygen saturation, and skin temperature for the first 2h of age.

Figure 9. Monitoring systems – ECG and temperature

Figure 10. Monitoring Systems – SpO2

All materials and equipment required for the conduct of the study will be provided to the participating sites by the lead site. All research team members at all sites will be trained on the placement and removal of the wireless and wired monitoring including appropriate cleaning and disinfecting protocols. Training on the use of the BioDash system will also be provided as part of the study training at all sites.

Vital Sign Monitoring:

If a baby is born via:

1. *Vaginal Delivery:* Following normal, vaginal delivery, the wireless skin sensor monitoring system (Anne Arc & RAD7 Limb,Sibel Health Inc - Masimo) will be immediately placed on the newborn. In order to promote the standard practice of bonding between newborn and mother the standard of care wired monitoring system (Infinity Monitor, Drager) will be placed on the newborn after 10-20 min of age.
2. *C-section:* Immediately before birth, the infant will be randomized for the type of monitoring system to be applied first: a) the wireless sensors (Anne Arc & RAD7 Limb,Sibel Health Inc - Masimo) or b) standard of care wired system (Infinity Monitor, Drager). In order to promote the standard practice of bonding between newborn and mother the second monitoring system will be placed on the newborn after 10-20 min of age.

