The research team will use the data collection software system called Biosensors Data Aggregation and Synchronization (BioDASH) developed by the Smart Hospital Project team in collaboration with iKinesia Inc. (Montreal, CANADA) to stream, visualize, and log data all in real-time from the standard of care wired monitoring system and the wireless monitoring system into a single study laptop (Figure 10) . Data from all monitoring devices will be aggregated and synchronized for display and logged into files for eventual offline analysis. See Figure 10 below for the BioDASH high-level system architecture and components. The BioDASH application is designed not to interfere with the patient monitor and will not store any protected health information. The streamed data logged by the application will be stored locally on the study laptop until the end of the recording period when it will be uploaded to a secure DropBox™ professional account created for the study by the Principal Investigator as well as a hard drive which will be kept in a locked cabinet in a room to which only RI-MUHC study personnel will be granted access. The data from all sites captured by BioDash will be uploaded to the secure DropBox™ professional account created for the study as well as a hard drive which will be kept in a locked cabinet in a room to which only study personnel will be granted access. The BioDash system as well as all the required devices will be provided to all participating sites by the Principal Investigator. All participating site study personnel will receive training on proper

placement of the sensors and wires, all data capturing systems and proper study conduct by the Principal Investigator and designated lead site study personnel.

[figure not shown]

Figure 11. BioDASH system architecture and components

[figure not shown]

Figure 12. Data obtained from each monitoring system will be de-identified and on a secure local server and then to a cloud before it is downloaded onto a secure data repository at the RI-MUCH for investigators' assessment.

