As part of the Smart Hospital Project, this Study and potential future research studies to improve the quality, accuracy and efficiency of monitoring neonates admitted in the NICU, the participants' information may be shared with academic or commercial third parties and used by the research team in other related research studies. Any use of the RI-MUHC and participating site's data in future research studies will be approved by competent research ethics boards and no data that could identify the participant will be shared. Participants at all participating sites will be asked to consent to the sharing of their data collected during this study as well as for use in future research in the field of neonatal care and monitoring. The participants' data will be kept confidential to the extent required by applicable laws. The research agreements with the participating sites will include all the terms and conditions required for the use and sharing of the data from participating sites.

4 Statistical Analysis and Rationale

Sample size: The proposed sample size is 100 newborns/site (n=600) to be recruited over 2 years from start of the Study at each site.

The expected mean and standard deviation are required for estimating the mean effects which is used to determine the absolute precision. In our first study with wireless sensors (see preliminary data) or *phase 1a*, 100 patient recordings (25 infants x 4 days) were expected but only 96 were obtained, resulting in a 4% drop-out rate. Further, the average coverage across wired HR signals was $98.7 \pm 2.2\%$, while that of wireless signals was $85.3 \pm 14.3\%$. Assuming a two-sided significance of 0.05, a study power of 0.9, and accounting for the drop-out rate of 0.04 in all calculations, we can expect an effect size of 2.7% in HR coverage, with the selected sample size of 600 infants. In the case of SpO₂ monitoring, the average coverage was $93.9 \pm 6.3\%$ in the wired system and $66.5 \pm 20.8\%$ in the wireless. In our proposed study, we

can thus expect a difference of 3.46% in SpO₂ coverage. For the statistical measures used to assess the agreement between the wired and wireless vital signals, the average findings from *phase 1a* are reported in the Table. Using the same parameters listed previously, the margin of error expected for each statistical measure in the proposed study can be found.

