Statistical measure		Correlation coefficient, C	Proportionality constant, k	Variance accounted for (VAF)	Mean difference (bias), d
Average result in phase 1a	Heart rate (HR)	0.96 ± 0.03	1.00 ± 0.00	91.5 ± 6.5%	0.04 ± 0.32 bpm
	Oxygen saturation (SpO ₂)	0.53 ± 0.23	1.01 ± 0.01	18.9 ± 20.8%	1.43 ± 1.4%
Expected margin of error	Heart rate (HR)	0.01	0.00	1.24%	0.06 bpm
	Oxygen saturation (SpO ₂)	0.04	0.00	3.97%	0.26%

Statistical analytical approach: Descriptive analyses will first be applied to the demographic data. Accuracy analysis of the wireless system to capture the vital signs will be done by using a statistical measure of the strength of a linear relationship between the two systems (correlation coefficient), a measurement of the steepness of this correlation (slope), the ratio of explained and target variance (variance accounted for), and a Bland-Altman plot analysis to evaluate *bias* between the mean differences and estimate an agreement interval.

Each participating site has the facilities and capacity to provide the estimated number of infants to establish feasibility, safety, and accuracy of the device. The wireless device sensors and system being used in the study is approved by Health Canada for research on neonates. Each site will obtain approval from their local and country specific health authorities, as required.

5 Ethical, Legal and Regulatory Considerations

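### Aim 2c counts wired-detected events that the wireless system misses, with no allowance for measurement error and no reference value, so even two equally accurate sensors would be expected to show some misses

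*Combined protocol and SAP*

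**What the plan says.** Section 2.2 (Aims) introduces the safety outcomes with "The following outcomes will be measured for both wired and wireless systems". Item c is then worded in one direction only: "Clinically significant events detected by the wired system (HR < 100 bpm or SpO₂ < 80%) but missed by the wireless system". Items a and b concern skin and pain, so 2c is the only safety outcome about detection.

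Section 3.3.4 (Data Collection) has the one other event definition, used for telling the clinical team: "HR < 100 bpm or SpO₂ <85% (after the first 10 minutes of life) with sinusoidal wave as detected on either monitoring system". It too is a plain cut, without a duration or a rule for matching events between systems. Its SpO₂ cut differs from that in Aim 2c. The two passages must be reconciled, but that is a separate matter.

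The design is paired: "Each newborn enrolled in the Study will be monitored simultaneously by both the standard of care (control) wired vital sign monitoring system". On handling, section 3.3.4 says "Data from all monitoring devices will be aggregated and synchronized for display and logged into files for eventual offline analysis".

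The analysis text in section 4 covers correlation, slope, variance accounted for and a "Bland-Altman plot analysis to evaluate *bias* between the mean differences and estimate an agreement interval". It has no method for Aim 2c. The power statement there ("Assuming a two-sided significance of 0.05, a study power of 0.9, and accounting for the drop-out rate of 0.04 in all calculations") is applied to signal coverage and the agreement measures, not to missed events.

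**The concern.** Every event in the count is there because the wired reading fell below a fixed cut. Among events near the cut, that selection favours moments when the wired error happened to be negative. The wireless reading at the same moment has its own error and tends to lie closer to the true value, which may be above the cut. The wireless system is then recorded as having missed an event although it was no less accurate. Synchronising the signals corrects timing, not noise.

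As worded, a wired 79% with a wireless 81% can count the same as a wired 65% with no wireless reading at all. The first pair says little about safety; the second says a great deal. Section 2.3 links the device to preventing catastrophic events after birth, so readers will take this count as evidence on whether the sensor can be trusted. A bare number cannot tell them which kind of miss they are looking at.

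**Working it through.** The documents give no expected miss rate, limit or sample size for Aim 2c, so there is no figure to reproduce. The check asks what the plain reading gives when neither sensor is at fault.

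**1. Two identical, unbiased SpO₂ sensors (simulation, 4 million dips per scenario).** All inputs are assumptions except the 80% cut.
- True nadir: T = 95 − Exp(mean depth), with mean depth 3, 5 or 8 points.
- Wired W = T + e₁ and wireless S = T + e₂, with independent normal errors of SD 1 to 3 points.
- Miss share = P(S ≥ 80 | W < 80).

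| Error SD | depth 3 | depth 5 | depth 8 |
|---|---|---|---|
| 1 | 19% | 11% | 7% |
| 1.4 | 26% | 16% | 10% |
| 2 | 37% | 22% | 14% |
| 3 | 52% | 33% | 21% |

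The reverse share, P(W ≥ 80 | S < 80), agrees with the forward share in every cell to within half a percentage point. With ten wired events in the whole trial, the chance of at least one miss is 1 − (1 − miss share)^10: about 52% at a 7% share and over 99% at 52%.

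**2. What reduces it.**
- *Shared error.* If half of the error variance is common to both sensors, the corner values 7% and 52% become 5% and 38%. If 80% is common, they become about 3% and 25%.
- *Depth.* At SD 1.4 and mean depth 5, wired readings below 75% are missed by an equal sensor about 0.1% of the time. The effect is concentrated at the cut.

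**3. Event-level version.** Simulated dips were centred near the cut, with autocorrelated noise (all assumed).
- SpO₂ noise SD 0.5 / 1.4 / 3.0: about 12% / 33% / 51% missed with no duration or matching rule.
- HR noise SD 0.32 / 1 / 4 bpm: about 3.5% / 8% / 36%.
- A 10 s minimum duration with a 15 s matching window still leaves 7.2% at SpO₂ SD 0.5 and 24.6% at SD 1.4. The reverse direction gives 7.8% and 22.4%. A duration rule alone does not remove the problem.

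**4. Cross-check from the Phase 1a correlations in section 4.** Treat two equal sensors as bivariate normal with correlation ρ, so that miss share = 1 − P(both < cut)/P(wired < cut). With the cut at the lowest 5% / 1% / 0.1% of readings (assumed):
- HR, ρ = 0.96: 23% / 30% / 37%.
- SpO₂, ρ = 0.53: 74% / 86% / 94%.

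These are not forecasts. The correlations come from NICU infants with an earlier chest sensor and include any real wireless error.

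**5. Why the allowance must not come from the trial's own paired differences.** Take depth 5, wired SD 1, and a tolerance of twice the SD of the paired difference.
- Wireless SD 1: tolerance 2√(1² + 1²) = 2.8 points; misses fall from 11% to 0.3%.
- Wireless SD 8: tolerance 2√(1² + 8²) = 16.1 points; misses fall from 31% to 0.9%. A far noisier sensor looks almost clean.
- An equal-sensor benchmark from the same SD also fails. It assigns each sensor SD √((1² + 8²)/2) = 5.7 and expects 57% misses, against 31% observed.

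With a fixed margin of 3 points, used only for illustration, the share of wired events with the wireless reading above 83% is 0.2% at wireless SD 1, 12% at SD 5 and 20% at SD 8. The reverse direction also responds. At wireless SD 5, 25% of wired events have no wireless counterpart, but 53% of wireless events have no wired counterpart.

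**The case against.** The strongest reply is that the protocol never writes the rule tested here. It speaks of clinically significant events and of missing them, and defines neither term. A reader might infer that the plan scores a miss at every instant when the wired reading is below the cut and the wireless reading is not. The text does not say so, and this point rests only on the plain reading. The reply does not remove the problem, since the event-level versions in step 3 also give counts above zero.

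The second reply is that much of this would be cured by counting the reverse direction. That is largely right. Equal sensors give equal discordance both ways, so the reverse table supplies a reference without an assumed error SD. It does not by itself separate shallow straddling from deep failure, for which the paired readings are needed.

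Third, the size is assumed throughout, and the main simulation compares one reading per dip although recording is continuous. This stands.

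Fourth, no decision hangs on the count. Section 3.2 presents the study as groundwork for a later trial, agreement and gaps are reported alongside, and the logged signals allow later reclassification. This also stands, and it limits the consequence. But a classification chosen after the discordant events have been seen is less convincing than one fixed beforehand.

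**Conclusion.** The point holds as a matter of interpretation. With at least partly independent errors and some true values near the cut, Aim 2c gives an expected count above zero for two equally accurate sensors, and the plan offers nothing to compare that count with.

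Only the direction is firm. The 7% to 52% range for SpO₂ depends on an assumed error SD of 1 to 3 points, assumed event depths and independent errors. It shrinks when errors are shared and is negligible for deep events. For HR the share is a few per cent at noise of 0.32 to 1 bpm and larger only with noisier signals.

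Two stronger readings are tempting and are not supported. One is that the wireless system is set up to fail its safety aim: no acceptance limit or test is attached to 2c, so nothing can be failed. The other is that the range above forecasts this trial's miss rate: the documents give no within-infant error or event-depth data from which to forecast it.

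**What to change.** Keep the event cuts and keep counting every discordant event. Add one paragraph to section 4, before the data are analysed, that does the following.

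1. Places each wired event without a wireless counterpart in one of three classes:
   - (a) no valid wireless reading although the sensor was on;
   - (b) wireless above the cut by no more than a fixed margin for that signal;
   - (c) wireless above the cut by more than that margin.
2. States the margin for HR and for SpO₂ in advance, from a source other than this trial's paired differences. Neither the margin nor any benchmark should be built from the trial's own wired-wireless difference SD, because a noisier wireless sensor would then widen its own allowance.
3. Lists, for each event, the depth of the wired reading and the simultaneous wireless reading.
4. Gives the same table in the reverse direction (wireless below the cut, wired not) as the reference for what equal sensors would produce. Similar counts both ways are what equal sensors would give; they do not prove equality, so the two tables should be read with the listed values.

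The same paragraph should say what constitutes an event and how events are matched between systems, since neither is defined now.

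The cost is that paragraph and some extra tabulation of signals already being logged. No new data, participants or change to clinical alerting is needed. No discordant event is dropped, so nothing is hidden by the classification.
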